**Table 3. Summary of adverse events by study group**

Adverse events	Procalcitonin		Control		Total
Number of participants	XXXX		XXXX		XXXX
Total number of events	XXXX		XXXX		XXXX
Grading of adverse events	1-2	3-4	1-2	3-4	
Symptoms, n/N (%)					
Septic thrombophlebitis	X/XX (X.X)	X/XX (X.X)	X/XX (X.X)	X/XX (X.X)	X/XX (X.X)
Catheter-associated urinary tract infection	X/XX (X.X)	X/XX (X.X)	X/XX (X.X)	X/XX (X.X)	X/XX (X.X)
Skin reaction	X/XX (X.X)	X/XX (X.X)	X/XX (X.X)	X/XX (X.X)	X/XX (X.X)
Diarrhea	X/XX (X.X)	X/XX (X.X)	X/XX (X.X)	X/XX (X.X)	X/XX (X.X)
Allergic reaction	X/XX (X.X)	X/XX (X.X)	X/XX (X.X)	X/XX (X.X)	X/XX (X.X)
Others (e.g. hospital acquired infections)					

### 3.5. Relationship of AEs to procalcitonin arm versus control arm

**Table 4. AE relationship to study group**

Adverse events	Procalcitonin		Placebo		Total
Number of related AEs (Yes)	XXXX		XXXX		XXXX
Total number of events	XXXX		XXXX		XXXX
Symptoms, n/N (%)					
Septic thrombophlebitis	X/XX (X.X)	X/XX (X.X)	X/XX (X.X)	X/XX (X.X)	X/XX (X.X)

**STATISTICAL ANALYSIS PLAN**

Catheter-associated urinary tract infection	X/XX (X.X)				
Skin reaction	X/XX (X.X)				
Diarrhea	X/XX (X.X)				
Allergic reaction	X/XX (X.X)				
XXX	X/XX (X.X)				
Others (e.g. hospital acquired infections)					

**Table 5. Summary of severe adverse events by study group**

Severe adverse events	Procalcitonin		Control		Total
Number of participants	XXXX		XXXX		XXXX
Total number of events	XXXX		XXXX		XXXX
Grading of adverse events					
Events, n/N (%)					
Deaths related to the study intervention such as death directly related to the early stopping of antibiotics or complications of prolonged use of antibiotics	X/XX (X.X)	X/XX (X.X)	X/XX (X.X)	X/XX (X.X)	X/XX (X.X)

**Table 6. SAE relationship to study group**

Severe adverse events	Procalcitonin		Control		Total
Number of participants	XXXX		XXXX		XXXX
Total number of events	XXXX		XXXX		XXXX
Grading of adverse events					
Events, n/N (%)					
Deaths (related to intervention)	X/XX (X.X)	X/XX (X.X)	X/XX (X.X)	X/XX (X.X)	X/XX (X.X)

**3.6 Microbiological analysis**

Phenotypic and genotypic data analysis of the bacterial isolates

**3.6.1 Antimicrobial Susceptibility Testing (AST) Analysis Plan**

## STATISTICAL ANALYSIS PLAN

### Descriptive Statistics

Antimicrobial susceptibility testing (AST) results will be categorised as susceptible (S), intermediate (I), or resistant (R) based on the breakpoints provided by CLSI guidelines. Any missing data will be handled appropriately and noted in the analysis.

Resistance patterns for each antibiotic will be summarised, including multidrug-resistant (MDR), extensively drug-resistant (XDR), and pandrug-resistant (PDR) bacteria. Frequencies and percentages of susceptible, intermediate, and resistant isolates will be reported for each antibiotic and bacterial species.

A summary table will be presented with the resistance rates for each antibiotic tested.

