### 2.1.3 Secondary objectives and endpoints

- To assess if procalcitonin guided de-escalation reduces antibiotic **consumption** and days of therapy with antibiotics.

- Consumption of antibiotics expressed as the Defined Daily Dosage (DDD)

*Definition of DDD: The basic definition for a defined daily dose is the assumed average maintenance dose per day for a drug used in its main indication in adults. Antibiotic use using the WHO DDD definition ([https://www.whocc.no/atc\\_ddd\\_index/](https://www.whocc.no/atc_ddd_index/)) will be determined for the most frequently prescribed Drugs in Bangladesh*

- Days of therapy with antibiotics (DOT)

Definition of DOT: One DOT represents the administration of a single antibiotic on a given day regardless of the number of doses administered or dosage strength. If a patient receives more than one antibiotic it will be added on with DOT of the first antibiotic. (Dalton et al. 2015)

- Number of days of parenteral antibiotic during hospitalisation period
- Number of days of antibiotic treatment during the hospitalisation period.

- To assess the safety of procalcitonin guided de-escalation of treatment
  - Overall mortality, mortality-associated with recurrent infection, and non-lethal recurrent infections.
- To assess the effect of procalcitonin guided de-escalation on length of hospital stay
  - Duration of hospital stay (ICU/ general ward)
- To determine the spectrum of antimicrobial resistance among bacteria identified in clinical specimens from Bangladeshi patients hospitalized with sepsis
  - Bacterial isolates from blood cultures will be identified, tested for antibiotic susceptibility. In a subset of antibiotic resistant isolates, genetic correlates of resistance will be assessed (A comprehensive microbiological analysis plan is provided in section 3.6).
- To compare the patient care costs between study arms
  - Direct medical costs of prescribed antibiotics, the PCT assay and hospital stay costs.

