### Comparative Analysis

Comparative analysis will be conducted between drug-resistant and drug-susceptible bacteria. Chi-square or Fisher's exact tests will be used, depending on the data distribution. A p-value of  $<0.05$  will be considered statistically significant.

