**STATISTICAL ANALYSIS PLAN**
**Table 8. Summary of culture positivity by culture type**

There are XX number of culture positive. Of XX, there were XX in Procalcitonin and XX were in Control.

Culture type	Out of total	Of culture positive
Blood, n/N (%)	X/X (X.XX)	X/X (X.XX)
Urine, n/N (%)	X/X (X.XX)	X/X (X.XX)
Sputum, n/N (%)	X/X (X.XX)	X/X (X.XX)
Pus, n/N (%)	X/X (X.XX)	X/X (X.XX)
Blister Fluid, n/N (%)	X/X (X.XX)	X/X (X.XX)
XXX	X/X (X.XX)	X/X (X.XX)

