**Table 13. Summary of bacterial species in different culture positive**

Species name	Blood	Urine	Sputum	Pus	Blister Fluid	Total
Acinetobacter spp., n (%)	X(X.XX)	X(X.XX)	X(X.XX)	X(X.XX)	X(X.XX)	X(X.XX)
Burkh. pseudomallei, n (%)	X(X.XX)	X(X.XX)	X(X.XX)	X(X.XX)	X(X.XX)	X(X.XX)
Burkhodelria cepacia, n (%)	X(X.XX)	X(X.XX)	X(X.XX)	X(X.XX)	X(X.XX)	X(X.XX)
Enterococ. faecalis, n (%)	X(X.XX)	X(X.XX)	X(X.XX)	X(X.XX)	X(X.XX)	X(X.XX)
Esch. coli, n (%)	X(X.XX)	X(X.XX)	X(X.XX)	X(X.XX)	X(X.XX)	X(X.XX)
Klebsiella pneumoniae, n (%)	X(X.XX)	X(X.XX)	X(X.XX)	X(X.XX)	X(X.XX)	X(X.XX)
Pseudomonas aeruginosa, n (%)	X(X.XX)	X(X.XX)	X(X.XX)	X(X.XX)	X(X.XX)	X(X.XX)
Pseudomonas spp., n (%)	X(X.XX)	X(X.XX)	X(X.XX)	X(X.XX)	X(X.XX)	X(X.XX)
Salmonella typhi, n (%)	X(X.XX)	X(X.XX)	X(X.XX)	X(X.XX)	X(X.XX)	X(X.XX)
Staphylococcus aureus, n (%)	X(X.XX)	X(X.XX)	X(X.XX)	X(X.XX)	X(X.XX)	X(X.XX)

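### Section 3.6.1 counts isolates with no first-isolate rule and plans tests with no allowance for several isolates per patient, and Section 2.1.3 leaves it unclear which specimens the resistance endpoint covers.

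*SAP*

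**What the plan says.** Section 2.1.3 states the objective as "To determine the spectrum of antimicrobial resistance among bacteria identified in clinical specimens from Bangladeshi patients hospitalized with sepsis". The endpoint line directly beneath it is narrower: "Bacterial isolates from blood cultures will be identified, tested for antibiotic susceptibility". The same line sends the reader to Section 3.6 for the detail ("A comprehensive microbiological analysis plan is provided in section 3.6"), so the specimen scope and the counting unit are meant to be settled in this SAP.

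Section 3.6.1 then sets out the following:

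- **Specimens.** Table 8 has one row each for blood, urine, sputum, pus and blister fluid, plus an open row. Table 13 has one column for each of these five types and a Total column across them.
- **Resistance tables.** Tables 10, 11, 14 and 15 give susceptible, resistant and intermediate results by drug, drug class or species. None has a specimen column or a restriction to blood.
- **Counting unit.** "Frequencies and percentages of susceptible, intermediate, and resistant isolates will be reported for each antibiotic and bacterial species". No rule covers repeat cultures or the same organism from two sites in one patient.
- **Tests.** "Comparative analysis will be conducted between drug-resistant and drug-susceptible bacteria", by chi-square or Fisher's exact test with a 0.05 threshold. Risk factors for resistance are then examined by a multivariable model such as logistic regression, reported as adjusted odds ratios with 95% intervals. No clustering, random-effect or robust-variance term is named.

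Section 3.3 does limit the resistance subgroup (pre-defined subgroup 3) to the admission or initial specimen, which gives a patient-level classification. That rule is not carried into Section 3.6.

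**The concern.** Two things are left open, and they compound each other.

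The first is scope. The endpoint line points to blood, while the objective and the tables of Section 3.6 point to all clinical specimens. Because the resistance tables have no specimen split, they cannot yield a blood-only result as laid out.

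The second is the unit. Once several specimen types are admitted, one patient can contribute the same strain from blood and urine. Counted by isolate, that patient appears twice in the resistance percentages. If the tests use the same unit, every patient-level risk factor is duplicated along with the isolate. Chi-square, Fisher's exact test and ordinary logistic regression all assume independent rows, so P values would be too small and odds-ratio intervals too narrow. Chance associations could then be reported as risk factors for resistance.

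**Working it through.** **The plan's own figures.** The SAP gives no isolate count, duplication rate or precision target for this endpoint. The only figure to check against is the 0.05 significance level.

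**Inputs**
- Nominal level: 0.05, critical value 1.96 (Section 3.6.1, Comparative Analysis).
- *f*, the share of culture-positive patients with two isolates of the same strain: not in the SAP; assumed 0.10 to 0.60.
- *ρ*, the within-patient agreement (concordance) of the two results, used as a correlation: not in the SAP; assumed 0.8 to 1.0.
- The factor tested is a patient characteristic, hence identical for both isolates.

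**Formulas.** With *m* isolates per patient (1 or 2):
- E[m] = 1 + f
- E[m²] = (1 − f) + 4f = 1 + 3f
- Design effect: DEFF = 1 + (E[m²]/E[m] − 1) × ρ
- True error of the nominal 5% test = 2 × (1 − Φ(1.96/√DEFF))

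**Results**

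| f | E[m²]/E[m] | DEFF, ρ = 0.8 | True error | DEFF, ρ = 1.0 | True error |
|---|---|---|---|---|---|
| 0.10 | 1.3/1.1 = 1.182 | 1.145 | 6.7% | 1.182 | 7.1% |
| 0.30 | 1.9/1.3 = 1.462 | 1.369 | 9.4% | 1.462 | 10.5% |
| 0.60 | 2.8/1.6 = 1.750 | 1.600 | 12.1% | 1.750 | 13.8% |

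The last entry in full: 1.96/√1.75 = 1.482, and 2 × (1 − Φ(1.482)) = 0.138.

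**Check by simulation.** The chi-square test was simulated with 100 and with 160 culture-positive patients (assumed numbers), half exposed to a patient-level factor with no true effect, true resistance 50% and ρ = 1.
- Two copies in 30% of patients: rejection in 10.8% and 10.7% of runs, against 10.5% from the formula.
- One isolate per patient: 5.5% and 4.6%, close to the nominal 5%.

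The excess error therefore comes from the duplicates, and counting one isolate per patient removes it.

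**The case against.** The case against has real substance.

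- **The endpoint is not simply blood.** A reader might infer that Section 3.6 departs from a blood-only endpoint. The objective itself says clinical specimens, so the five-specimen tables agree with it and conflict only with the endpoint line. The documents do not show which was intended.
- **The specimen tables do not pool.** Tables 8 and 13 separate the specimen types; only the Total column of Table 13 adds them up. The missing split matters in the resistance tables.
- **Not every table counts isolates.** Table 12 is headed as a number of antibiotics. Table 9 uses culture positives as its denominator, and the sentence introducing Table 8 divides these by arm, so they may be patients.
- **The unit of the tests is not stated.** The comparative paragraph says bacteria, and the regression paragraph names no unit. One row per patient is compatible with both. The isolate as unit is an inference from the counting rule.
- **The direction depends on the comparison.** The inflation applies to patient-level factors. If blood and urine isolates from the same patients were compared, positive within-patient correlation would make an unpaired test conservative.
- **An upward bias in resistance rates is not shown.** A reader might infer that resistant infections are cultured more often and that the percentages are therefore too high. Nothing in the SAP says so. If duplication is equally common in resistant and susceptible infections, the expected percentage does not move.

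These points narrow the concern but do not remove it. The scope is stated in two ways, the one sentence that names a unit names isolates, and no rule or method deals with repeat isolates.

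**Conclusion.** The concern holds in a limited form. Section 2.1.3 states the specimen scope of the resistance endpoint in two ways, and the resistance tables of Section 3.6.1 cannot separate blood from other specimens. Isolates are counted without a first-isolate rule, and the planned tests and regression make no allowance for several isolates per patient.

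If the isolate is the unit of those analyses, tests of patient-level factors are anticonservative. The true error is about 7 to 14% in place of 5%, assuming that 10 to 60% of culture-positive patients give two isolates of the same strain with concordance 0.8 to 1.0. The SAP supports neither end of that range, and the effect vanishes if no patient contributes a strain twice.

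This bears on a secondary endpoint and its risk-factor analysis. The primary analysis of length of therapy and the sample size are not affected. The change should be made, but the trial's main conclusion does not depend on it.

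**What to change.** 1. In Section 2.1.3, reconcile the objective with the endpoint line and state which specimens govern the resistance endpoint.
2. In Section 3.6.1, count the first isolate per patient and species, and say whether each table's denominator is patients, cultures or isolates.
3. In Tables 10, 11, 14 and 15, report blood isolates separately from the other specimen types.
4. Run the comparative tests and the risk-factor regression with one row per patient. If all isolates are kept, use standard errors clustered by patient, for example from GEE, and replace the plain chi-square and Fisher tests accordingly.

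The cost is a few sentences in the SAP, one de-duplication step by patient number, and smaller denominators in some tables.

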### Comparative Analysis

Comparative analysis will be conducted between drug-resistant and drug-susceptible bacteria. Chi-square or Fisher's exact tests will be used, depending on the data distribution. A p-value of  $<0.05$  will be considered statistically significant.

### Multivariate Analysis

Multivariate analysis, such as logistic regression, will be conducted to identify risk factors associated with antimicrobial resistance. Potential confounders and covariates will be adjusted for in the models, and results will be presented as adjusted odds ratios with 95% confidence intervals.

### Reporting Guidelines

The results will be presented in visual formats such as bar charts, heatmaps, and antibiograms to clearly convey resistance profiles. Data will be summarised visually to aid in understanding the susceptibility patterns.

**Table 7. AST Analysis Plan**

Step	Description
1. Descriptive Statistics	Categorise AST results as susceptible, intermediate, or resistant. Handle missing data appropriately. Summarise resistance patterns for each antibiotic, including MDR, XDR, and PDR bacteria. Present frequencies and percentages in a summary table.
2. Comparative Analysis	Conduct comparative analysis between drug-resistant and drug-susceptible bacteria using Chi-square or Fisher's exact tests. A p-value of $<0.05$ will be considered statistically significant.
3. Multivariate Analysis	Perform logistic regression or other multivariate analyses to identify risk factors for antimicrobial resistance. Adjust for confounders and present adjusted odds ratios (AORs) with 95% confidence intervals.
4. Reporting Guidelines	Present results visually using bar charts, heatmaps to clearly convey resistance profiles.

**STATISTICAL ANALYSIS PLAN**
**Table 8. Summary of culture positivity by culture type**

There are XX number of culture positive. Of XX, there were XX in Procalcitonin and XX were in Control.

Culture type	Out of total	Of culture positive
Blood, n/N (%)	X/X (X.XX)	X/X (X.XX)
Urine, n/N (%)	X/X (X.XX)	X/X (X.XX)
Sputum, n/N (%)	X/X (X.XX)	X/X (X.XX)
Pus, n/N (%)	X/X (X.XX)	X/X (X.XX)
Blister Fluid, n/N (%)	X/X (X.XX)	X/X (X.XX)
XXX	X/X (X.XX)	X/X (X.XX)

**Table 9. Summary of Species name**

Species name	Of culture positive
Acinetobacter spp. , n/N (%)	X/X (X.XX)
Burkh. pseudomallei, n/N (%)	X/X (X.XX)
Burkhodelria cepacia, n/N (%)	X/X (X.XX)
Enterococ. faecalis, n/N (%)	X/X (X.XX)
Esch coli, n/N (%)	X/X (X.XX)
Klebsiella pneumoniae, n/N (%)	X/X (X.XX)
Pseudomonas aeruginosa, n/N (%)	X/X (X.XX)
Pseudomonas spp. , n/N (%)	X/X (X.XX)
Salmonella typhi, n/N (%)	X/X (X.XX)
Staphylococcus aureus, n/N (%)	X/X (X.XX)
Staphylococcus epidermidis, n/N (%)	X/X (X.XX)
Strept. pneumoniae, n/N (%)	X/X (X.XX)
Strept. pyogenes, n/N (%)	X/X (X.XX)
XXXX	X/X (X.XX)

**Table 10. Summary of drug sensitivity only in ESC**

Drug name	S	R	I	Total
Amoxicillin (AMO), n (%)	X(X.XX)	X(X.XX)	X(X.XX)	X(X.XX)
Amikacin (AMI), n (%)	X(X.XX)	X(X.XX)	X(X.XX)	X(X.XX)
Ampicillin (AML), n (%)	X(X.XX)	X(X.XX)	X(X.XX)	X(X.XX)
Azithromycin (AZM), n (%)	X(X.XX)	X(X.XX)	X(X.XX)	X(X.XX)
Aztreonam (ATM), n (%)	X(X.XX)	X(X.XX)	X(X.XX)	X(X.XX)

## STATISTICAL ANALYSIS PLAN

Cefepime (FEP), n (%)	X(X.XX)	X(X.XX)	X(X.XX)	X(X.XX)
Cefixime (CFM), n (%)	X(X.XX)	X(X.XX)	X(X.XX)	X(X.XX)
Ceftriaxone (CRO), n (%)	X(X.XX)	X(X.XX)	X(X.XX)	X(X.XX)
Ciprofloxacin (CIP), n (%)	X(X.XX)	X(X.XX)	X(X.XX)	X(X.XX)
Colistin (CT), n (%)	X(X.XX)	X(X.XX)	X(X.XX)	X(X.XX)
Gentamycin 10 (CN), n (%)	X(X.XX)	X(X.XX)	X(X.XX)	X(X.XX)
Gentamycin 120 (CN), n (%)	X(X.XX)	X(X.XX)	X(X.XX)	X(X.XX)
Levofloxacin (LEV), n (%)	X(X.XX)	X(X.XX)	X(X.XX)	X(X.XX)
Ceftazidime (CAZ), n (%)	X(X.XX)	X(X.XX)	X(X.XX)	X(X.XX)
Ceftazidimeavibactum, n (%)	X(X.XX)	X(X.XX)	X(X.XX)	X(X.XX)
Cotrimoxazole(SXT) , n (%)	X(X.XX)	X(X.XX)	X(X.XX)	X(X.XX)
Meropenem (MEM) , n (%)	X(X.XX)	X(X.XX)	X(X.XX)	X(X.XX)
Nitrofurantoin(F) , n (%)	X(X.XX)	X(X.XX)	X(X.XX)	X(X.XX)
Piperacillin/Tazobactam(TZP) , n (%)	X(X.XX)	X(X.XX)	X(X.XX)	X(X.XX)
Polymyxin B (PB) , n (%)	X(X.XX)	X(X.XX)	X(X.XX)	X(X.XX)
Tetracycline (TE) , n (%)	X(X.XX)	X(X.XX)	X(X.XX)	X(X.XX)
Tigecycline (TGC) , n (%)	X(X.XX)	X(X.XX)	X(X.XX)	X(X.XX)
Tobramycin (TOB), n (%)	X(X.XX)	X(X.XX)	X(X.XX)	X(X.XX)
XXXX	X(X.XX)	X(X.XX)	X(X.XX)	X(X.XX)
XXXX	X(X.XX)	X(X.XX)	X(X.XX)	X(X.XX)

**Table 11. Summary of drug sensitivity grouping only in ESC**

Drug name	S	R	I	Total
Aminoglycoside, n (%)	X(X.XX)	X(X.XX)	X(X.XX)	X(X.XX)
Penicillin, n (%)	X(X.XX)	X(X.XX)	X(X.XX)	X(X.XX)
Macrolids, n (%)	X(X.XX)	X(X.XX)	X(X.XX)	X(X.XX)
Monobactams, n (%)	X(X.XX)	X(X.XX)	X(X.XX)	X(X.XX)
Quinolones, n (%)	X(X.XX)	X(X.XX)	X(X.XX)	X(X.XX)
Carbapenem, n (%)	X(X.XX)	X(X.XX)	X(X.XX)	X(X.XX)
Cephalosporin+Beta lactam inhibitor, n (%)	X(X.XX)	X(X.XX)	X(X.XX)	X(X.XX)
Cephalosporins, n (%)	X(X.XX)	X(X.XX)	X(X.XX)	X(X.XX)
Nitrofurans, n (%)	X(X.XX)	X(X.XX)	X(X.XX)	X(X.XX)
Penicillin+Beta lactam inhibitor, n (%)	X(X.XX)	X(X.XX)	X(X.XX)	X(X.XX)
Polymyxins, n (%)	X(X.XX)	X(X.XX)	X(X.XX)	X(X.XX)
Sulfonamides, n (%)	X(X.XX)	X(X.XX)	X(X.XX)	X(X.XX)

**STATISTICAL ANALYSIS PLAN**

Tetracyclines, n (%)	X(X.XX)	X(X.XX)	X(X.XX)	X(X.XX)
XXXX	X(X.XX)	X(X.XX)	X(X.XX)	X(X.XX)
XXXX	X(X.XX)	X(X.XX)	X(X.XX)	X(X.XX)

**Definition of MDR Bacteria**

For Multi-Drug Resistant (MDR) bacteria, all of them are MDR as resistant (R) to two or more classes of antibiotics (Table 12).

**Table 12. Summary of MDR Bacteria**

Species name	MDR number of antibiotics
Acinetobacter spp.	XX
Burkh. pseudomallei	XX
Burkholderia cepacia	XX
Enterococ. faecalis	XX
Esch. coli	XX
Klebsiella pneumoniae	XX
Pseudomonas aeruginosa	XX
Pseudomonas spp.	XX
Salmonella typhi	XX
Staphylococcus aureus	XX
Staphylococcus epidermidis	XX
Strept. pneumoniae	XX
Strept. pyogenes	XX
XX	XX

**Table 13. Summary of bacterial species in different culture positive**

Species name	Blood	Urine	Sputum	Pus	Blister Fluid	Total
Acinetobacter spp., n (%)	X(X.XX)	X(X.XX)	X(X.XX)	X(X.XX)	X(X.XX)	X(X.XX)
Burkh. pseudomallei, n (%)	X(X.XX)	X(X.XX)	X(X.XX)	X(X.XX)	X(X.XX)	X(X.XX)
Burkhodelria cepacia, n (%)	X(X.XX)	X(X.XX)	X(X.XX)	X(X.XX)	X(X.XX)	X(X.XX)
Enterococ. faecalis, n (%)	X(X.XX)	X(X.XX)	X(X.XX)	X(X.XX)	X(X.XX)	X(X.XX)
Esch. coli, n (%)	X(X.XX)	X(X.XX)	X(X.XX)	X(X.XX)	X(X.XX)	X(X.XX)
Klebsiella pneumoniae, n (%)	X(X.XX)	X(X.XX)	X(X.XX)	X(X.XX)	X(X.XX)	X(X.XX)
Pseudomonas aeruginosa, n (%)	X(X.XX)	X(X.XX)	X(X.XX)	X(X.XX)	X(X.XX)	X(X.XX)
Pseudomonas spp., n (%)	X(X.XX)	X(X.XX)	X(X.XX)	X(X.XX)	X(X.XX)	X(X.XX)
Salmonella typhi, n (%)	X(X.XX)	X(X.XX)	X(X.XX)	X(X.XX)	X(X.XX)	X(X.XX)
Staphylococcus aureus, n (%)	X(X.XX)	X(X.XX)	X(X.XX)	X(X.XX)	X(X.XX)	X(X.XX)

## STATISTICAL ANALYSIS PLAN

Staphylococcus epidermidis, n (%)	X(X.XX)	X(X.XX)	X(X.XX)	X(X.XX)	X(X.XX)	X(X.XX)
Strept. pneumoniae, n (%)	X(X.XX)	X(X.XX)	X(X.XX)	X(X.XX)	X(X.XX)	X(X.XX)
Strept. pyogenes, n (%)	X(X.XX)	X(X.XX)	X(X.XX)	X(X.XX)	X(X.XX)	X(X.XX)

**Table 14. Summary of bacterial species in CRO**

Species name	S	R	I	Total
Acinetobacter spp., n (%)	X(X.XX)	X(X.XX)	X(X.XX)	X(X.XX)
Enterococ. faecalis, n (%)	X(X.XX)	X(X.XX)	X(X.XX)	X(X.XX)
Esch coli, n (%)	X(X.XX)	X(X.XX)	X(X.XX)	X(X.XX)
Klebsiella pneumoniae, n (%)	X(X.XX)	X(X.XX)	X(X.XX)	X(X.XX)
Pseudomonas aeruginosa, n (%)	X(X.XX)	X(X.XX)	X(X.XX)	X(X.XX)
Salmonella typhi, n (%)	X(X.XX)	X(X.XX)	X(X.XX)	X(X.XX)
Staphylococcus aureus, n (%)	X(X.XX)	X(X.XX)	X(X.XX)	X(X.XX)
Strept. pneumoniae, n (%)	X(X.XX)	X(X.XX)	X(X.XX)	X(X.XX)
Strept. pyogenes, n (%)	X(X.XX)	X(X.XX)	X(X.XX)	X(X.XX)

**Table 15. Summary of bacterial species in CXM**

Species name	S	R	I	Total
Burkh. pseudomallei, n (%)	X(X.XX)	X(X.XX)	X(X.XX)	X(X.XX)
Esch coli, n (%)	X(X.XX)	X(X.XX)	X(X.XX)	X(X.XX)
Klebsiella pneumoniae, n (%)	X(X.XX)	X(X.XX)	X(X.XX)	X(X.XX)
Staphylococcus aureus, n (%)	X(X.XX)	X(X.XX)	X(X.XX)	X(X.XX)

**Table 16. Summary of Initial Diagnosis**

Initial Diagnosis	Frequency n (%)
Enteric Fever	X(X.XX)
Intra-abdominal Infection	X(X.XX)
Lower Resp Tract Infection	X(X.XX)
Meningoencephalitis	X(X.XX)
Skin and Soft Tissue Infection	X(X.XX)
Undifferentiated Sepsis	X(X.XX)
Upper Resp Tract Infection	X(X.XX)
Urinary Tract Infection	X(X.XX)

---

## STATISTICAL ANALYSIS PLAN

### 3.6.2 Analysis plan of the whole genome sequencing data

#### Whole Genome Sequencing

Bacterial isolates will undergo whole genome sequencing using MicrobesNG's Short Read service. The sequencing will be performed using Illumina technology, providing  $2 \times 250$  bp paired-end reads with a minimum coverage of 30X. Genomic DNA will be extracted from the bacterial isolates using standardised protocols, and sequencing libraries will be prepared according to the manufacturer's instructions. If required, MicrobesNG will also handle the DNA extraction at no extra cost.

#### Bioinformatics Analysis

Raw sequencing data will be processed using bioinformatics tools and pipelines to ensure high-quality genome assemblies. The analysis will include the following steps:

1. Quality Control: Raw reads will be assessed for quality using tools like FastQC. Low-quality reads and adapter sequences will be trimmed using software such as Trimmomatic.
2. Genome Assembly: High-quality reads will be assembled using de novo assemblers like SPAdes or Velvet. The quality of assemblies will be evaluated using metrics such as N50 and total assembly length.
3. Annotation: Assembled genomes will be annotated to identify genes, coding sequences, and other genomic features using tools like Prokka or Bakta.
4. Comparative Genomics: Resistance genes and mutations conferring antibiotic resistance will be identified using NCBI AMR finder+. Plasmid sequences will be identified to examine any common plasmids or other mobile genetic elements carrying AMR genes.
5. Phylogenetic Analysis: Phylogenetic trees will be constructed to examine the evolutionary relationships among the bacterial isolates. This will help in understanding the transmission dynamics and evolutionary history of MDR bacteria in the study population.

